APPENDIX C. PATIENT'S GLOBAL IMPRESSION OF CHANGE (PGIC) SCALE

Date	Patient Name	Date of
Birth		

Chief Complaint (Presenting Problem):

Since beginning treatment at this clinic, how would you describe the change (if any) in ACTIVITY LIMITATIONS, SYMPTOMS, EMOTIONS, and OVERALL QUALITY OF LIFE, related to your painful condition? Please circle the number below that matches your degree of change since beginning care at this clinic for the above stated chief complaint.

No change	Almost the same	A little better	Somewhat better	Moderately better	Better	A great deal better
1	2	3	4	5	6	7

Explanation:

1 = No change (or condition has got worse)	5 = Moderately better, and a slight but noticeable		
2 = Almost the same, hardly any change at all	change		
3 = A little better, but no noticeable change	6 = Better, and a definite improvement that has made a real and worthwhile difference		
4 = Somewhat better, but the change has not made any real difference	7 = A great deal better, and a considerable improvement that has made all the difference		

Patient's signature: X

Do not write in this box - FOR OFFICE USE ONLY.
NOTE TO HEALTH CARE PROVIDER
A significant, favorable change is a score of 5- 7
No significant change is a 1-4 response.
Note, this is a dichotomous scale (5-7 = yes; 1-4 = no).
A 2-point change is significant from their last reported score.
Reference: Hurst H, Bolton J. Assessing the clinical significance of change scores recorded on subjective outcome measures. Journal of Manipulative
Physiological Therapeutics (IMPT) 2004;27:26-35.

APPENDIX D. EXAMPLE SAS CODE

The following sample SAS code pertains to the primary efficacy ANCOVA analysis:

ODS OUTPUT DIFFS = XXX LSMEANS = XXX

PROC MIXED DATA = XXX;

CLASS TREATMENT MIGRAINETYPE PREVENTIVEMEDICATION;

MODEL CHG = TREATMENT MIGRAINETYPE PREVENTIVEMEDICATION BASE;

LSMEANS TREATMENT / CL PDIFF;

RUN;

The following SAS code pertains to the main MMRM analysis:

ODS OUTPUT DIFFS = XXX LSMEANS = XXX

PROC MIXED DATA=XXX;

CLASS USUBJID MONTH TREATMENT MIGRAINETYPE PREVENTIVEMEDICATION;

MODEL CHG=BASE MONTH TREATMENT MIGRAINETYPE PREVENTIVEMEDICATION TREATMENT*MONTH;

REPEATED MONTH/SUBJECT=USUBJID TYPE=UN;

LSMEANS TREATMENT TREATMENT*MONTH/PDIFF CL ALPHA=0.05;

RUN;

The following SAS code pertains to the sensitivity MMRM analysis:

ODS OUTPUT DIFFS = XXX LSMEANS = XXX

PROC MIXED DATA=XXX;

CLASS USUBJID MONTH TREATMENT MIGRAINETYPE PREVENTIVEMEDICATION;

MODEL CHG=BASE MONTH TREATMENT MIGRAINETYPE PREVENTIVEMEDICATION TREATMENT*MONTH BASE*MONTH;

REPEATED MONTH/SUBJECT=USUBJID TYPE=UN;

LSMEANS TREATMENT TREATMENT*MONTH/PDIFF CL ALPHA=0.05;

RUN;

The following SAS code pertains to the MI analysis:

PROC MI DATA=XX SEED=98765 OUT=MI_OUT NIMPUTE=100 MAXIMUM=... 28 28 28 MINIMUM=... 0 0 0 0;

CLASS TRTMI MIGRAINETYPE PREVENTIVEMEDICATION;

FCS REG(V0=TRTMI MIGRAINETYPE PREVENTIVEMEDICATION /DETAILS) NBITER=100;

FCS REG(V1=TRTMI MIGRAINETYPE PREVENTIVEMEDICATION V0 /DETAILS) NBITER=100;

FCS REG(V2=TRTMI MIGRAINETYPE PREVENTIVEMEDICATION V0 V1/DETAILS) NBITER=100;

FCS REG(V3=TRTMI MIGRAINETYPE PREVENTIVEMEDICATION

V0 V1 V2/DETAILS) NBITER=100; VAR TRTMI MIGRAINETYPE PREVENTIVEMEDICATION V0 V1 V2 V3;

RUN;

where TRTMI is the placebo reassigned treatment group.

The output dataset from the below SAS code will contain the estimate of the mean difference and the standard error of the estimate from each of the 100 datasets

ODS OUTPUT DIFFS=DIFF LSMEANS=LSM; PROC MIXED DATA=UPDATED_MI_OUT METHOD=REML; BY IMPUTATION; CLASS TREAT MIGRAINETYPE PREVENTIVEMEDICATION; MODEL CHG=BASE TREAT MIGRAINETYPE PREVENTIVEMEDICATION; LSMEANS TREAT/DIFF;

RUN;

where TREAT is the planned randomized treatment group.

SAS PROC MIANALYZE code is as follows;

ODS OUTPUT PARAMETERESTIMATES=PARMEST; PROC MIANALYZE DATA=MIXED_OUT ALPHA=0.05 THETA0=0; BY TREAT; MODELEFFECTS ESTIMATE; STDERR STDERR;

RUN; where TREAT is the planned randomized treatment group.

The following SAS code pertains to the logistic regression analysis:

PROC LOGISTIC DATA = XXX;

CLASS TREATMENT (REF = '1') MIGRAINETYPE PREVENTIVEMEDICATIONUSE / PARAM = REF;

MODEL RESPONSE (EVENT = '1') = TREATMENT MIGRAINETYPE PREVENTIVEMEDICATIONUSE BASELINE;

RUN;

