3. STUDY DESIGN

3.1. General Study Design and Study Schematic Diagram

This is a multicenter, randomized, double-blind, placebo-controlled study with an open-label treatment period to evaluate the efficacy, safety, and tolerability of monthly and quarterly sc fremanezumab for the preventive treatment of migraine in adults. The study will consist of a screening visit, a baseline period (4 weeks), a 12-week double-blind treatment period, a 12-week open-label treatment period, and a follow-up period lasting approximately 3 months after the last dose of IMP (ie, 2 months after the end of treatment [EOT]/early termination [ET] visit). A follow-up visit 3 months after the last dose of fremanezumab will occur for ADA blood sample collection.

The total duration of patient participation in the study is planned to be approximately 9 months.

This study will include female and male patients, aged 18 to 70 years, inclusive, with a history of migraine (as defined by the International Classification of Headache Disorders, 3rd revision [ICHD-3] criteria [IHS 2018, CMAPS 2016]) for at least 12 months prior to screening and a prospectively documented diagnosis of migraine confirmed via a review of headache data recorded daily in an electronic headache diary device during a 28-day baseline period.

Up to 30% of patients will be allowed to continue on a stable dose of 1 preventive migraine medication listed in [Appendix K](#) for migraine prevention or for other chronic conditions that they were using before screening (patients must have been taking a stable dose of these medications for at least 2 months of consecutive use prior to screening and do not expect to change dosing regimens or to change to another medication during the treatment phase of the study). Patients will be allowed to use acute medications to treat breakthrough migraines as needed, with the exception of medications containing opioids and barbiturates, which cannot be used on more than 4 days during the screening period for the treatment of migraine or for any other reason. Traditional Chinese therapy (including herbal medicine) and acupuncture are allowed if the patient is on a stable dose/regimen for at least 2 months (consecutive) before screening.

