9.5.4.1. Primary Efficacy Analysis

The primary comparison will be made between the combined fremanezumab groups versus the placebo group in the primary efficacy variable: mean change from baseline in the monthly average number of migraine days during the 12-week double-blind treatment period after the 1st dose of IMP. The primary efficacy analysis will consider all fremanezumab-treated patients as 1 group (ie, regardless of dosing regimen or migraine type).

An estimand in general includes the following 4 interrelated attributes: population of interest, variable (endpoint) of interest, intercurrent events (ICEs) along with the strategy for handling ICEs, and population-level summary for the endpoint.

The estimand selected for the primary analysis will assess the 12-week monthly average number of migraine days as initially randomized in the mITT analysis set.

The ICEs that may affect the efficacy endpoint will include instances where a patient early terminates from the IMP, receives the wrong IMP due to medication errors, or receives a rescue medication due to worsening symptoms. If observations are collected after the occurrences of the ICEs, the observations will be included in the calculation of the primary endpoint for the primary analysis.

The population-level summaries would be the adjusted mean changes from baseline in monthly average number of migraine days for the treatment groups and corresponding 95% confidence intervals.

An analysis of covariance (ANCOVA) will be performed, including treatment and stratification factors of migraine type (CM vs EM) and preventive medication use as fixed factors, as well as baseline number of migraine days as a covariate in the model. A 95% confidence interval for the treatment difference between the combined fremanezumab groups versus the placebo group will be derived through an appropriate contrast, and p-values for the comparison will be presented. Further details will be presented in the statistical analysis plan.

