2. STUDY DESIGN

2.1. General Design

This is a multicenter, randomized, double-blind, placebo-controlled study with an open-label treatment period to evaluate the efficacy, safety, and tolerability of monthly and quarterly sc fremanezumab for the preventive treatment of migraine in adults. The study will consist of a screening visit, a baseline period (4 weeks), a 12-week double-blind treatment period, a 12-week open-label treatment period, and a follow-up period lasting approximately 3 months after the last dose of IMP (ie, 2 months after the end of treatment [EOT]/early termination [ET] visit). A follow-up visit 3 months after the last dose of fremanezumab will occur for ADA blood sample collection.

The total duration of patient participation in the study is planned to be approximately 9 months.

This study will include female and male patients, aged 18 to 70 years, inclusive, with a history of migraine (as defined by the International Classification of Headache Disorders, 3rd revision [ICHD-3] criteria [IHS 2018, CMAPS 2016]) for at least 12 months prior to screening and a prospectively documented diagnosis of migraine confirmed via a review of headache data recorded daily in an electronic headache diary device during a 28-day baseline period.

Up to 30% of patients will be allowed to continue on a stable dose of 1 preventive migraine medication listed in the study protocol for migraine prevention or for other chronic conditions that they were using before screening (patients must have been taking a stable dose of these medications for at least 2 months of consecutive use prior to screening and do not expect to change dosing regimens or to change to another medication during the treatment phase of the study). Patients will be allowed to use acute medications to treat breakthrough migraines as needed, with the exception of medications containing opioids and barbiturates, which cannot be used on more than 4 days during the screening period for the treatment of migraine or for any other reason. Traditional Chinese therapy (including herbal medicine) and acupuncture are allowed if the patient is on a stable dose/regimen for at least 2 months (consecutive) before screening.

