6.2. Primary Efficacy Endpoint and Analysis

6.2.1. Primary Estimand

The primary estimand will be the difference in adjusted means between fremanezumab group and placebo group in the population that comprises the patients in the double-blind mITT analysis set for the change from baseline in the monthly average number of migraine days during the 12-week period after the 1st dose of IMP. The intercurrent events (ICEs) that may affect the efficacy endpoint will be handled as per Table 1.

Intercurrent event	Strategy
Patient early terminates from the IMP	Treatment policy ¹
Patient receives the wrong IMP due to medication errors	Treatment policy ¹
Patient receives a rescue medication due to worsening symptoms	Treatment policy ¹

Table 1: Intercurrent Event Strategies: Primary Estimand

¹Treatment policy: if observations are collected after the occurrences of the ICEs, the observations will be included in the calculation of the primary endpoint for the primary analysis.

The baseline values will be derived using formula (3). The post baseline values will be derived using formula (1), and *the change* is calculated as *postbaseline – baseline value*.

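### The example ANCOVA and MI code gives preventive users a weight of 50% against a 30% cap, so arm-level adjusted means, SEs and intervals do not reflect the mITT stratum mix; the treatment comparison is unaffected

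*SAP*

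**What the plan says.** **Code.** The primary model in SAP Appendix D is "MODEL CHG = TREATMENT MIGRAINETYPE PREVENTIVEMEDICATION BASE", with treatment, migraine type and preventive medication as class variables and no interactions. Arm means come from "LSMEANS TREATMENT / CL PDIFF". The MI analysis model uses "LSMEANS TREAT/DIFF" and both MMRM blocks use "LSMEANS TREATMENT TREATMENT*MONTH/PDIFF CL ALPHA=0.05". None of these carries a weighting option, and neither document states stratum weights in its text.

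**Stratum shares.** Protocol 3.1: "Up to 30% of patients will be allowed to continue on a stable dose of 1 preventive migraine medication". SAP 2.1 repeats the cap. Protocol 9.1 and SAP 2.4 require at least 30% of each migraine type, so CM may be anywhere from 30% to 70%.

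**What is reported.** Protocol 9.5.4.1 sets the estimand in the mITT set and says: "The population-level summaries would be the adjusted mean changes from baseline in monthly average number of migraine days for the treatment groups", with 95% confidence intervals. SAP 6.2.1 defines the primary estimand as the difference in adjusted means "in the population that comprises the patients in the double-blind mITT analysis set". SAP 6.2.2 presents the LS mean, SE and 95% CI for each arm as well as for the difference. SAP 6.2.3.4 does so for each regimen, without p-values.

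**The concern.** An LS mean is a prediction for a reference population. The default here holds baseline migraine days at the observed mean but gives each level of each class factor the same weight. For preventive use that means half the patients on a preventive, which the protocol's cap rules out. The arm-level adjusted changes from baseline are planned results that readers will compare with raw means and with other trials. If preventive users change by a different amount at the same baseline, the arm means are pulled towards the smaller stratum. Even if they do not, the intervals are wider than they would be for the enrolled mix, because the smaller stratum is over-weighted. SAP 6.3.2 carries the same method over to the first, second and fourth secondary estimands.

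**Working it through.** **Inputs.**
- Preventive share p: at most 0.30 (Protocol 3.1, SAP 2.1). Both pivotal studies had 21% (Protocol 1.2.2.2).
- CM share c: 0.30 to 0.70 (SAP 2.4).
- n = 186 per comparison arm (SAP 2.4).
- SD 4.45 days and difference 1.6 days. These appear only in the protocol's amendment log (entry for Section 9.1, Amendment 01). The current sample-size text is redacted, so I treat them as assumptions.

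**The plan's own figure.** n = 2 x (1.960 + 1.282)² x 4.45² / 1.6² = 2 x 10.507 x 19.80 / 2.56 = 162.6, so 163 per group. 163 / 0.88 = 185.2, so 186 per group and 372 in total. The assumed inputs reproduce the stated 163 and 372.

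**Weight error.** Preventive use: 0.50 against at most 0.30, so at least 0.20. At 21% it is 0.29, and preventive users count 0.50 / 0.21 = 2.4 times their share. Migraine type: between -0.20 and +0.20, and zero if enrolment is 50:50.

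**Arm SE.** With strata balanced across arms and treated as unrelated to each other and to baseline:

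Var = SD² x [1/n + (0.5 - p)² / (2n p(1 - p)) + (0.5 - c)² / (2n c(1 - c))]

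The observed-margin SE is 4.45 / √186 = 0.326.

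| p | c | SE, equal weights | Increase |
|---|---|---|---|
| 0.30 | 0.50 | 0.342 | 4.7% |
| 0.30 | 0.30 | 0.356 | 9% |
| 0.21 | 0.50 | 0.365 | 12% |

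First row: 1/186 + 0.04 / (372 x 0.21) = 0.005376 + 0.000512 = 0.005888; √0.005888 x 4.45 = 0.342.

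The percentages depend on neither SD nor n. With c = 0.5 the ratio is √[1 + (0.5 - p)² / (2p(1 - p))]: √1.0952 = 1.047 at p = 0.30, and √1.2535 = 1.120 at p = 0.21. The ratio rises as p falls, and correlation with the other model terms can only add to it, so 4.7% is the floor under the cap. In days it is small: 1.96 x (0.3415 - 0.3263) = 0.03 on the CI half-width.

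**Arm centre.** Shift = (0.5 - p) x b_prev + (0.5 - c) x b_CM, the same in both arms. The coefficients, conditional on baseline migraine days, are not documented. If b_prev were 1 day and c = 0.5, the shift would be 0.20 day at p = 0.30 and 0.29 day at p = 0.21. Over assumed ranges of p from 0.10 to 0.30, b_prev from 0.5 to 2 days and b_CM from -1 to +1 day, it runs from -0.1 to +1.0 day. It is zero if the coefficients are zero or cancel.

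**Treatment difference.** The model is additive, so the stratum terms are identical in both arm means and cancel under any common weights.

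**Check on simulated data** (SAP ANCOVA, 328 completers, SD 4.45, true difference 1.6, c = 0.5, p about 0.30, b_prev = +1 day, b_CM = 0; averages of 300 runs):

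| | Equal weights | Observed margins |
|---|---|---|
| Placebo LS mean (SE) | -1.99 (0.362) | -2.19 (0.347) |
| Fremanezumab LS mean (SE) | -3.59 (0.362) | -3.79 (0.347) |
| Difference (SE) | -1.60 (0.491) | -1.60 (0.491) |

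The raw placebo mean was -2.19, which matches the observed-margin column. The SE ratio is 0.362 / 0.347 = 1.04; rounding of stratum sizes put the simulated preventive share at 100/328 = 30.5%.

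**The case against.** **The governing estimand is the difference.** SAP 6.2.1 attaches the population wording to the difference between arms, and the SAP's introduction says it prevails over the protocol where they differ. This stands as a limit: the estimand's estimate, SE, CI and p-value are the same under either weighting. It does not remove the mismatch, because SAP 6.2.2 still plans arm-level LS means with SEs and CIs, and Protocol 9.5.4.1 calls them the population-level summaries for the mITT estimand.

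**Equal weighting is a recognised convention, and the code is only an example.** True, but no text says that an equal-stratum reference population is intended, and nothing overrides the default.

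**Other tables reveal the mix.** SAP 6.1 plans by-month descriptive statistics by treatment group, and SAP 5.3 reports preventive use and migraine type. These help a careful reader, but they do not replace an adjusted 12-week arm mean with its interval.

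**Stronger readings to avoid.** A reader might infer that both strata are certainly mis-weighted; the documents guarantee this only for preventive use. A reader might also set an arm-level shift against the 1.6-day planned effect. That comparison fails: the shift is common to both arms and cancels from the effect, and its size rests on undocumented coefficients.

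**Conclusion.** The point holds as a minor reporting correction. Under the Appendix D ANCOVA and MI code, arm-level adjusted means are computed for a population with half its patients on preventives, against a maximum of 30%. The arm SE is at least about 4.7% larger than for the observed mix, and about 12% larger if preventive use matches the 21% of the pivotal studies with CM at 50%. Those percentages rest on the stratum shares alone; the absolute SEs also rest on the SD of 4.45 days from the amendment log. The arm centres may shift, by an amount the documents cannot fix and which may be zero.

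A reader might infer that the primary result is biased or the trial's power reduced. The documents do not support that: with no treatment-by-stratum interaction in the model, the difference, its CI, the p-value, the sample size and the testing hierarchy are untouched.

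**What to change.** 1. **ANCOVA and MI code:** add the OM option to the LSMEANS statements, so that stratum levels are weighted by their observed shares in the set analysed (double-blind mITT for the ANCOVA, ITT for the MI analysis).
2. **MMRM code:** do not add a bare OM. Month is also a class factor there, and OM would weight months by their row counts. If later months have missing rows, that departs from the average over 3 months in SAP 6.2.3.1 and could move the MMRM treatment difference. Apply observed margins to migraine type and preventive use only, with months kept equal, through an OM= data set with balanced months or through ESTIMATE statements.
3. **SAP 6.2.2:** add one sentence saying that arm-level LS means are standardised to the observed stratum mix of the analysis set.

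The cost is one option in the ANCOVA and MI code, a slightly longer change in the MMRM code, and one sentence. The primary test does not change.
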